## 1.0 TRIAL SUMMARY

Abbreviated Title	Adjuvant HNC anti-PD1 chemoradiation phase II study
Trial Phase	Phase II
Clinical Indication	High and Intermediate risk resected HNC
Trial Type	2 arm, non-randomized
Type of control	Historical
Route of administration	IV
Trial Blinding	None

Treatment Groups	High risk and Intermediate risk
Number of trial subjects	80
Estimated enrollment period	3 years
Estimated duration of trial	8 years (5 years disease free survival (DFS) + 3-year enrollment period)
Duration of Participation for subjects	5 years

## 2.0 TRIAL DESIGN

[figure not shown]
### 2.1 Trial Design

This study will be a two arm phase II trial including 80 patients with head and neck squamous cell carcinoma (HNSCC) eligible for resection. Patients who are identified to be clinically high risk (see inclusion) prior to resection will be screened and consented to receive 1 dose Pembrolizumab followed by resection. Post-resection, patients will be stratified and if high risk features are confirmed by pathology (extracapsular extension [ECE], or positive margins), patients will receive concurrent weekly Cisplatin, daily radiation and every three week Pembrolizumab as shown in schema. If those enrolled prior to resection are found to not have high risk pathological features, they will go on to receive radiation and Pembrolizumab. Eight patients from each group will be enrolled as part of a lead-in on a rolling basis to determine the safety of this combination with stopping rules if expected toxicity is exceeded. There will be a fair proportion of patients who are identified to be high risk prior to resection but do not have confirmed high risk pathologic features. Therefore, we expect that using our criteria, that at least 50% (or 40 patients) will have high risk features requiring chemotherapy in addition to radiation (CRT) and Pembrolizumab while the remaining intermediate risk patients will receive radiation and Pembrolizumab. For correlative studies, archived or fresh biopsy samples and resection tissue will be assessed by H&E and IHC for immune phenotype. Blood samples will also be collected as described in section 7 for correlative studies. Patients will be followed approximately weekly during treatment,

then monthly for the first 3 months following treatment and then every 3 months thereafter for the first two years. A repeat PET/CT or CT scan will be performed at 3 months post-treatment to assess for early relapse. Patients will be assessed every 3 months for the first 2 years and then every 6 months for the next 3 years for disease free survival (DFS) and overall survival (OS).

### 2.2 Trial Diagram

## Flow Diagram

## 3.0 OBJECTIVES & HYPOTHESES

### 3.1 Primary Objectives & Hypotheses

**(1) Objective:** Determine the frequency and severity of side effects of Pembrolizumab when administered in combination with radiation alone or Cisplatin and radiation therapy (CRT) in patients undergoing adjuvant treatment for resected HNSCC.

- Hypothesis:** Combining Pembrolizumab with concurrent Cisplatin and radiation will be safe, causing minimal interruption to standard of care therapy in patients with resected HNSCC.

**(2) Objective:** To estimate the 1 and 3 year disease free survival (DFS) combining Pembrolizumab with adjuvant CRT in patients with resected high risk HNSCC.

- **Hypothesis:** Combining Pembrolizumab to concurrent Cisplatin and radiation will increase DFS in patients with resected HNSCC relative to historic data as there is not a current comparison in this trial.

**(3) Objective:** To estimate the 1 and 3 year disease free survival (DFS) combining Pembrolizumab with adjuvant radiation in patients with resected intermediate risk HNSCC.

- **Hypothesis:** Combining Pembrolizumab to radiation will increase DFS in patients with resected HNSCC relative to historic data as there is not a current comparison in this trial.

### 3.2 Secondary Objectives & Hypotheses

**(1) Objective:** To estimate the 1 and 3 year overall survival (OS) combining Pembrolizumab with adjuvant CRT in patients with resected high risk HNSCC.

- **Hypothesis:** Combining Pembrolizumab to concurrent Cisplatin and radiation will increase OS in patients with resected HNSCC relative to historic data as there is not a current comparison in this trial.

**(2) Objective:** To estimate the 1 and 3 year overall survival (OS) combining Pembrolizumab with adjuvant radiation in patients with resected intermediate risk HNSCC.

- **Hypothesis:** Combining Pembrolizumab to radiation will increase OS in patients with resected HNSCC relative to historic data as there is not a current comparison in this trial.

**(3) Objective:** Determine the change in distribution of the tumor immune microenvironment before and after Pembrolizumab administration in tumor biopsy tissue using markers of T cells and T cell activation including but not limited to CD4, CD8, CD38, HLA-DR, PD-1 and PD-L1.

- **Hypothesis:** Pembrolizumab administration will result in enhanced immune stimulation in tumors marked by T cell infiltration/activation.

**(4) Objective:** Determine the baseline adenosine receptor expression in HNSCC patients and the effect of PD-1 inhibition by Pembrolizumab in activated T cells combined with peripheral T cell activation by flow cytometry.

- **Hypothesis:** Pembrolizumab administration will result in increased adenosine receptor expression which will confer resistance to T cell activation.

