##### Tumor Microenvironment and Mechanism of Resistance to anti-PD-1

The tumor microenvironment exerts an immune suppressive role in cancer by limiting the capacity of T cells to accumulate among cancer cells resulting in immune-mediated cell death. Various aspects of the tumor microenvironment have been shown to limit T cell function: hypoxia, indoleamine 2,3-dioxygenase (IDO), adenosine and PGE2. The suppressive effects of adenosine and hypoxia on T lymphocytes are mediated by ion channels (Kv1.3 and KCa3.1). Both adenosine and PGE2 signal through their respective receptors, cAMP/PKA and their effect in mast cells is mediated by KCa3.1 channels. Evidence exists that alterations of the tumor microenvironment improve the efficacy of

immune checkpoint blockade. In a recent study in mice, the combination therapy of anti-PD1 with blockers of the adenosine receptor (A2AR) proved to be superior to anti-PD1 monotherapy. On the other hand, the anti-PD1 therapy could also make the immune cells more sensitive to the tumor microenvironment as it has been reported that PD1 blockade in mice increases the expression of A2AR in tumor infiltrating T lymphocytes (TILs). The goal of this collateral study is to determine whether (1) the tumor microenvironment and tumor microenvironment-related features of TILs at baseline (pre-drug) can be used as predictors of responders and non-responders; (2) anti-PD-1 treatment alters the characteristics of TILs making them more susceptible to the immune suppression of the tumor microenvironment with the consequent development of resistance to anti-PD-1 therapy; (3) unique alterations of T cell phenotype and function pre-drug or after therapy can be found in peripheral blood T cells.

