### **7.1.3.2.2 Immunohistochemistry/Immunofluorescence/RNA In Situ Hybridization**

Archived biopsy and resected tissue and if fresh resected tissue (Cincinnati only) will be shipped to University of Cincinnati for analysis. FFPE and Frozen sections will be used to analyze the immune cell phenotype (markers include but are not limited to CD4, CD8, PD-1, FOXP3, A2aR, PD-L1, CD73).

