#### Secondary Endpoints

Overall Survival (OS): defined as the time from randomization to death due to any cause. Subjects without documented death at the time of the final analysis will be censored at the date of the last follow-up. OS at 1 and 3 years will be used as secondary endpoints.

Locoregional Control: failure was defined as the reappearance of tumor in the original tumor bed or the development of cervical-node metastases after treatment.

Biomarker analysis including proportion of T cell population subsets before and after immunotherapy both in tumor tissue and peripheral blood.

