#### **8.2.4.4 Biomarker Assessments**

All biomarker measures will be summarized with descriptive statistics, i.e., percentages for categorical outcomes and means/medians for continuous outcomes, with corresponding standard errors and 95% confidence intervals. Responses will be tabulated by determined response and toxicities will be tabulated by type and grade. For IHC, the percentage of positive cells per area will be multiplied by the staining intensity for each tumor to determine quantitative expression pre- and post-treatment; a 25% change in expression will be considered a positive response. We will use descriptive statistics and graphical displays to evaluate change in serum markers and flow cytometry markers between pre- and post-treatment.

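### Secondary hypothesis 3.2(4) asserts a link between adenosine receptor expression and resistance to T cell activation, but no planned analysis relates the two measures

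*Combined protocol and SAP*

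**What the plan says.** Objective (4) in section 3.2 is to determine baseline adenosine receptor expression and "the effect of PD-1 inhibition by Pembrolizumab in activated T cells combined with peripheral T cell activation by flow cytometry". Its hypothesis is that "Pembrolizumab administration will result in increased adenosine receptor expression which will confer resistance to T cell activation". The subsection of 4.2.3.3 on resistance to anti-PD-1 gives a related study goal: to find out whether "anti-PD-1 treatment alters the characteristics of TILs making them more susceptible to the immune suppression of the tumor microenvironment", with resistance to therapy as the consequence.

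The analysis is in section 8.2.4.4: "All biomarker measures will be summarized with descriptive statistics, i.e., percentages for categorical outcomes and means/medians for continuous outcomes", with standard errors and 95% confidence intervals. For immunohistochemistry, "a 25% change in expression will be considered a positive response". For blood, "We will use descriptive statistics and graphical displays to evaluate change in serum markers and flow cytometry markers between pre- and post-treatment".

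Section 8.2.2 defines the matching secondary endpoint as "Biomarker analysis including proportion of T cell population subsets before and after immunotherapy both in tumor tissue and peripheral blood", which does not name the receptor. The receptor appears as an assay marker in section 7.1.3.2.2, for tissue sections: "markers include but are not limited to CD4, CD8, PD-1, FOXP3, A2aR, PD-L1, CD73".

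**The concern.** The hypothesis has two parts. The first, that the receptor rises after pembrolizumab, can be answered by a pre/post summary of one marker. The second, that the rise makes T cells resistant to activation, is a statement about how two measures move together. Summaries of each marker alone carry no information on that.

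At stake is what the trial can report on one of its own secondary hypotheses. Followed as written, 8.2.4.4 yields an average receptor change and an average activation change. A report could set the two side by side, but nothing in the planned output would show whether they are related. The samples that could show it are already being collected.

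**Working it through.** **The plan's own figure.** The documents give no sample size, effect size, alpha or power for objective 3.2(4), so there is nothing to reproduce. The check is a comparison of texts, followed by arithmetic under stated assumptions.

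**Texts side by side.**
- Hypothesis 3.2(4): receptor up, and the rise confers resistance to activation (two measures and a link).
- Section 8.2.4.4: percentages, means or medians, a 25% change rule for immunohistochemistry, and descriptive pre/post change. No correlation, regression or cross-tabulation.
- Section 8.2.2: T cell subset proportions before and after treatment. No receptor and no link.
- Exploratory objective 3.3(2): T cell function after anti-PD-1 treatment, not tied to the receptor.
- Section 4.2.3.3: the resistance idea as a goal, without a method.

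**Why separate summaries cannot show a link.** Take any set of paired data and reassign the activation results at random among patients, keeping each patient's pre and post values together. Every mean, median, percentage, standard error and interval for each marker is unchanged, while the association between the two changes can take a different size or sign. This needs no assumption about effect sizes.

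**Illustration with no link.** Assume independent changes and a mean receptor rise of 0.5 SD. The probability that one 95% CI excludes zero in that direction (one-sample t) is 0.869 at n = 40 and 0.993 at n = 80. The probability that both CIs exclude zero in the hypothesised directions depends on what mean activation does:
- Mean fall of 0.5 SD: 0.869² = 0.756 at n = 40; 0.993² = 0.986 at n = 80.
- No mean change: 0.869 × 0.025 = 0.022; 0.993 × 0.025 = 0.025.

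A simulation of the first case (5,000 runs) gave 75% and 99%. Across all simulated cases (shifts of 0.5 and 0.8 SD; 20, 40 and 80 pairs), a significant negative correlation between the two changes appeared in 2.4% to 2.8% of runs, about the 2.5% expected by chance. The paired analysis thus keeps its error rate whatever the mean shifts are. How often the separate summaries resemble the hypothesis depends on the assumed shifts.

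**What a paired analysis could deliver.** Fisher z, two-sided 0.05. CI half-width near r = 0: tanh(1.96/√(n − 3)). Correlation detectable with 80% power: tanh((1.96 + 0.84)/√(n − 3)). The numbers of pairs are assumptions; section 2.1 plans 80 patients, about 40 of them high risk.

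| Pairs | √(n − 3) | CI half-width | Detectable r |
|---|---|---|---|
| 20 | 4.12 | 0.44 | 0.59 |
| 40 | 6.08 | 0.31 | 0.43 |
| 80 | 8.77 | 0.22 | 0.31 |

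Power at given values is Φ(atanh(|r|)·√(n − 3) − 1.96):
- |r| = 0.45: 52% at n = 20 and 84% at n = 40.
- |r| = 0.30: 47% at n = 40 and 78% at n = 80.
- |r| = 0.40: 96% at n = 80.

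These figures are for a Pearson correlation of roughly normal changes.

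**The case against.** **The plan is descriptive and confirms nothing.** Section 8.2.4.4 sets no test or success rule, and the objective is worded as estimation. This stands. A reader might infer that the trial would usually appear to confirm a false link, citing the 76% and 99% above. The documents do not support that. There is no rule by which the hypothesis would be declared confirmed. The percentages also require mean activation to fall, whereas hypothesis 3.2(3) expects T cell activation in the tumour to rise. With no mean change in activation, the figure is about 2%.

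**A joint look is not excluded.** The objective uses the words combined with, and the graphical displays are undefined, so a plot of one change against the other is possible. True, but none is planned, and no estimate or interval would follow from it.

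**The hypothesis may be meant at the cell level.** Section 4.2.3.3 discusses adenosine acting through ion channels, objective 3.3(2) lists functional assays, and section 7.1.3.2.1 provides for functional analysis of blood cells. So a patient-level correlation is not the only way to examine the link. But none of these texts specifies an analysis relating function or activation to the receptor. The procedure manual, which was not available, is cited there for details of blood cell processing.

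**A correlation does not show that the receptor confers resistance.** Correct, and the fix is worded accordingly.

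**Conclusion.** The point holds as a gap between hypothesis and analysis: the output of 8.2.4.4 cannot address the second half of hypothesis 3.2(4). That follows from the texts and from the reassignment argument, not from any assumed effect size. Assumptions enter only in the precision of the remedy. With 40 pairs the detectable correlation is about 0.43, so a moderate link could be missed, and with 20 pairs only a strong one (about 0.59) would be found reliably.

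The importance is low. This is a correlative secondary objective with no bearing on the DFS or OS analyses, safety or patient management.

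**What to change.** Add one paragraph to 8.2.4.4 for objective 3.2(4):

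- Use patients with paired samples from before the pre-surgical dose and from before or at resection. Sections 7.1.2.7 and 7.1.3.2.1 already provide for both, and the interval precedes cisplatin and radiation.
- Name the compartment and assay for each measure. The receptor is listed for tissue sections, while the objective refers to peripheral activation by flow cytometry.
- Estimate the association between change in receptor expression and change in T cell activation, by Spearman correlation or by regression of post-dose activation on receptor change adjusted for baseline activation. Report the 95% CI and the number of evaluable pairs.
- Describe a negative association as supporting the link only if the 95% CI excludes zero. With no link, the point estimate alone is negative about half the time. Word the result as association, not as the receptor conferring resistance.
- Otherwise report only the receptor change.

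The simpler alternative is to reword the hypothesis to the receptor change alone.

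The cost is one SAP paragraph and one extra analysis, with no new samples or visits. The downside is limited precision and a claim that becomes harder to make.

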### 3.3 Exploratory Objectives

**(1) Objective:** Determine immunoregulatory activity in the serum including immune related cytokines including but not limited to IL-2 and IL-6.

**(2) Objective:** Study peripheral blood T cell and tumor infiltrating lymphocyte functionality (motility, calcium response to antigen presentation, ion channel function, cytotoxicity, apoptosis and cytokine release) to see if and what type of functionality is gained after anti-PD1 treatment.

**(3) Objective:** Assess the presence of myeloid derived suppressor cells, pro- and anti-inflammatory monocytes and dendritic cells in the blood and tissue at the different points of treatment as a

marker of prognosis using staining that would include, but not be limited to CD14, CD16, CD11c, CD1c, CD303, CD141, CD68, PDL-1, CD33, GR1, and HLA-DR.

**(4) Objective:** Assess disease free and overall survival at 5 years.

## 4.0 BACKGROUND & RATIONALE

### 4.1 Background

Refer to the Investigator's Brochure (IB)/approved labeling for detailed background information on MK-3475.

#### 4.1.1 Pharmaceutical and Therapeutic Background

The importance of intact immune surveillance in controlling outgrowth of neoplastic transformation has been known for decades. Accumulating evidence shows a correlation between tumor-infiltrating lymphocytes (TILs) in cancer tissue and favorable prognosis in various malignancies. In particular, the presence of CD8+ T-cells and the ratio of CD8+ effector T-cells / FoxP3+ regulatory T-cells seems to correlate with improved prognosis and long-term survival in many solid tumors.

The PD-1 receptor-ligand interaction is a major pathway hijacked by tumors to suppress immune control. The normal function of PD-1, expressed on the cell surface of activated T-cells under healthy conditions, is to down-modulate unwanted or excessive immune responses, including autoimmune reactions. PD-1 (encoded by the gene Pdcd1) is an Ig superfamily member related to CD28 and CTLA-4 which has been shown to negatively regulate antigen receptor signaling upon engagement of its ligands (PD-L1 and/or PD-L2). The structure of murine PD-1 has been resolved. PD-1 and family members are type I transmembrane glycoproteins containing an Ig Variable-type (V-type) domain responsible for ligand binding and a cytoplasmic tail which is responsible for the binding of signaling molecules. The cytoplasmic tail of PD-1 contains 2 tyrosine-based signaling motifs, an immunoreceptor tyrosine-based inhibition motif (ITIM) and an immunoreceptor tyrosine-based switch motif (ITSM). Following T-cell stimulation, PD1 recruits the tyrosine phosphatases SHP-1 and SHP-2 to the ITSM motif within its cytoplasmic tail, leading to the dephosphorylation of effector molecules such as CD3 $\zeta$ , PKC $\theta$ - and ZAP70 which are involved in the CD3 T-cell signaling cascade. The mechanism by which PD-1 down modulates T-cell responses is similar to, but distinct from that of CTLA-4 as both molecules regulate an overlapping set of signaling proteins. PD-1 was shown to be expressed on activated lymphocytes including peripheral CD4+ and CD8+ T-cells, B-cells, T regs and Natural Killer cells. Expression has also been shown during thymic development on CD4-CD8- (double negative) T-cells as well as subsets of macrophages and dendritic cells. The ligands for PD-1 (PD-L1 and PD-L2) are constitutively expressed or can be induced in a variety of cell types, including non-hematopoietic tissues as well as in various tumors. Both ligands are type I transmembrane receptors containing both IgV- and IgC-like domains in the extracellular region and contain short cytoplasmic regions with no known signaling motifs. Binding of either PD-1 ligand to PD-1 inhibits T-cell activation triggered through the T-cell receptor. PD-L1 is expressed at low levels on various non-hematopoietic tissues, most notably on vascular endothelium, whereas PD-L2 protein is only detectably expressed on antigen-presenting cells found in lymphoid tissue or chronic inflammatory

environments. PD-L2 is thought to control immune T-cell activation in lymphoid organs, whereas PD-L1 serves to dampen unwarranted T-cell function in peripheral tissues. Although healthy organs express little (if any) PD-L1, a variety of cancers were demonstrated to express abundant levels of this T-cell inhibitor. PD-1 has been suggested to regulate tumor-specific T-cell expansion in subjects with melanoma (MEL). It is now known that the PD-1/PD-L1 pathway plays a critical role in tumor immune evasion and two different PD-1 inhibitors, Pembrolizumab and nivolumab, are FDA approved for therapeutic intervention in melanoma (as well as squamous cell carcinoma of the lung for nivolumab).

Pembrolizumab specifically is a potent and highly selective humanized monoclonal antibody (mAb) of the IgG4/kappa isotype designed to directly block the interaction between PD-1 and its ligands, PD-L1 and PD-L2. Keytruda™ (Pembrolizumab) has recently been approved in the United States for the treatment of patients with unresectable or metastatic melanoma and disease progression following ipilimumab and, if BRAF V600 mutation positive, a BRAF inhibitor.

#### **4.1.2 Preclinical and Clinical Trial Data**

Refer to the Investigator's Brochure for Preclinical and Clinical data.

#### **4.1.3 Adjuvant treatment in Head and Neck Cancer**

Head and neck squamous cell carcinoma (HNSCC) is the sixth most common cancer worldwide. Although early stage tumors are often cured with surgery or radiation, up to 60% of patients present with locally advanced disease requiring multimodality treatment. Many patients with locally advanced disease will undergo upfront surgical resection, but unfortunately, the rate of relapse both locally and distantly after surgery alone is high, particularly in patients with high risk features (multiple lymph node involvement, extracapsular spread or those with positive surgical margins). Two pivotal studies by the EORTC and RTOG published in 2004 demonstrated increased progression free and overall survival in patients who received adjuvant concurrent Cisplatin and radiation albeit with higher toxicity over radiation alone. However, PFS and OS were only 47% and 53% respectively at 5 years and even lower if HPV positive patients were excluded. Follow-up meta-analysis by Bernier et al. in 2005 demonstrated that the only common characteristics between both studies who received benefit from the addition of chemotherapy to radiation were ECE and positive margins. Approximately 70% of the patients in the EORTC and 59% of RTOG study had one or both of these high risk features which may explain why overall survival benefit was seen in the EORTC trial only. When the data was pooled together from both studies, the risk of relapse in the high risk group was reduced by 42% whereas those without these features did not seem to benefit from the addition of chemotherapy. Currently standard of care per NCCN guidelines consists of chemotherapy and radiation for this high risk group and radiation only in those with intermediate features (multiple lymph node involvement, perineural invasion, etc). However, despite current standards, patients continue to have high rates of relapse in both groups. In fact, even patients (combined risk factors) who received CRT in the EORTC study had a DFS of only 48% at 5 years (54% at 2 years in the RTOG study) suggesting that novel treatments are necessary in order to improve outcomes in these patients.

